In addition to the well-known role of 5AR enzymes in conversion of testosterone to dihydrotestosterone, 5AR (and 5β-reductase) enzymes inactivate cortisol to 5-dihydrocortisol, which is then converted to the inactive elimination cortisol metabolite 5-tetrahydrocortisol (5a/b-THF) by 3-hydroxysteroid dehydrogenase. 5α-THF and 5β-THF each represent ≈20% of total urinary excretion of cortisol metabolites (Finken, Andrews et al. 1999). Dutasteride and finasteride treatment for 3 months in healthy subjects reduces levels of 5α-reduced cortisol urinary metabolites by over 95% without an increase in 5β-reduced cortisol metabolites resulting in an overall reduction of urinary cortisol metabolites but without a change in morning plasma or salivary cortisol (Upreti, Hughes et al. 2014). This recent finding suggests that 5AR inhibitors reduce overall adrenal cortisol output by reduction in rates of elimination with compensatory cortisol feedback reductions in further HPA axis activation and suggests that dutasteride would be expected to reduce the plasma ACTH to cortisol ratio. HPA effects are thus a second mechanism by which dutasteride could moderate alcohol intake which may be most relevant to patients with elevated stress, stress reactivity, anxiety or trauma (Blaine and Sinha 2017).

2.B.2. Preliminary studies.

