At the end of phase 1 treatment week 12 (visit 8) and phase 2 treatment week 24 (visit 14), subjects will complete a series of questionnaires and be interviewed by research staff concerning their alcohol consumption and alcohol-related symptomatology. For subjects who withdraw early and do not wish to continue with study visits/procedures, end-of-treatment evaluations will be administered at the time of withdrawal. Such subjects will also be invited to participate in-person or by telephone to provide drinking data for the 12-, 24-week time points in order to include this data in intent to treat analysis of the treatment phase.

2.C.4.d. Visits 15 and 16 (3- and 6-month Post-treatment Assessment): To evaluate the durability of treatment effects, patients will be invited to return to the clinic for a post-treatment assessment 3 and 6 months after completion of treatment (if unable to come in person a telephone interview will be conducted). Subjects will be contacted 6-8 weeks after end of treatment and following the 3-month follow-up visit to remind them of their follow-up appointment dates, reinforce maintaining their written drinking diary and to remind female subjects of the importance of continued use of effective contraception for 6 months following treatment. At each follow-up visit, subjects will complete self-report questionnaires and will be interviewed by the research staff. Blood samples for measurement of serum PEth, and 3α -diolG will be obtained. Subjects will be paid \$50 for participating in each post treatment visit.

2.C.5. Medical Management: A study physician will meet with each subject at the beginning of treatment. The PI will consult at least weekly with study staff to monitor potential study-related side effects and will be available to personally evaluate subjects with severe or persistent adverse effects. At each treatment encounter, subjects will receive brief counseling as part of medical management, described below.

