2.C.6.a. Laboratory/Medical Assessments: A physical examination, urinalysis, urine toxicology, serum bHCG (for women), CBC, and a chemistry panel (which includes electrolytes, liver enzymes [ASAT, ALAT, GGT], direct bilirubin, BUN, and creatinine) will be used to screen subjects for medical exclusion criteria. ASAT, ALAT will be repeated for subjects with elevations at baseline greater than 3x normal at weeks 6, 12, 18 and 24 (or until reduced to less than 3x normal). Weight, blood pressure and pulse will be obtained at each treatment visit. Urine will be tested every 6 weeks for drugs of abuse and HCG for women of reproductive potential. Blood will be archived for measurement of phosphatidylethanol (PEth) by a commercial testing lab as an objective measure of alcohol use. PEth is an alcohol-specific adduct catalyzed by phospholipase D from ethanol and phosphatidylcholine in membranes of red blood cells and is not affected by liver or kidney disease, age or sex. It is a sensitive and specific metabolite which is produced in direct response to use of alcohol during the past 20-30 days (Viel, Boscolo-Berto et al. 2012). PEth levels are correlated with the amount of alcohol consumed (Aradottir, Asanovska et al. 2006) and correlate better with daily diary drinking reports than carbohydrate deficient transferrin or gamma glutamyl transferase (de Bejczy, Lof et al. 2015, Walther, de Bejczy et al. 2015). Blood for PEth will be collected at screening, and weeks 6, 12, 18 and 24. Serum 3α-diolG will be measured using a commercial ELISA kit as a biochemical measure of 5AR inhibition by dutasteride. 3α -diolG is a major metabolite of testosterone and is more abundant that DHT especially in women and has been shown to decrease in parallel

with DHT following finasteride treatment in men (Rittmaster, Stoner et al. 1989, Gormley, Stoner et al. 1990) and has been used to monitor the reduction of 5AR activity in women treated with finasteride (Wong, Morris et al. 1995, Falsetti, Gambera et al. 1999). Serum testosterone, estradiol, progesterone, cortisol, ACTH and sex hormone binding globulin will be measured using commercial immunoassays to evaluate changes in these steroid hormones during treatment with dutasteride. Blood for 3α -diolG and steroid hormones will be collected at screening and weeks 6, 12, 18 and 24.

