Study Visit	V1 Screen	V2 Baseline	V 3-7	phase 2 baseline	V 9-13	V14	V15-16
Time relative to Medication		Start medication	wks 2, 4,6,8,10	wk 12 end phase 1	wks 14, 16,18,20,22	wk 24 end phase 2	3- and 6- mo follow- up
Medical History, demographics, AUDIT, SCID, FHAM, ACES, TESI, STAI-trait, Clinical screening labs, blood for DNA and research analytes Physical Exam & Clinician review of Medical History	x						

TLFB, PHQ-9, CIWA, MTR	X	Х	X	X	Χ	X	Χ
Vital signs & weight	Х	Х	X	Х	Х	Х	Х
DMQ, AEQ, SIP	Х			Х		Х	Х
Study outcome blood samples	Х		wk 6	Х	wk 18	Х	Χ
Urine drug screen, HCG (women), PACS	Х		wk 6	Х	wk 18	Х	Х
STAI-state, PSS		Х					
STAI-trait, PSS				Х		Х	Х
Daily IVR call		Х	wk 1-4	wk 9-12		wk 21-24	
Side Effect Checklist (SAFTEE)		Х	Х	Х	Х	Х	Х
Medical Management		Х	Х	Х	Х	Х	
Alcohol SCID past 1 month				Х		Х	Х

The IVR system will use the same procedures we have used in the recently completed dutasteride study and prior UConn Health studies of topiramate (Kranzler, Armeli et al. 2016). a) Daily drinking diary: Every evening, as part of the IVR daily diary, patients will record their alcohol consumption as the number of standard drinks in each of three categories of alcoholic beverages: beer, wine, liquor. Patients are asked to report separately drinking from yesterday and any drinking during the current day, up until the time of the IVR report. This allows us to examine lagged associations with mood and life event triggers. b) Daily mood: Patients will be asked to rate as part of the daily IVR their mood using an adjective checklist. The checklist consists of 9 adjectives (Larsen and Diener 1992) with each rated on a 5-point scale (0 = "not at all" to 4 = "extremely"). Three adjectives for each of three mood state dimensions provide measures of positive mood, negative mood and activated mood. Subjects will also be asked to report their self-efficacy for managing life problems. c) Daily Events: Participants will be asked whether they experienced a list of nine possible daily events (3 stressful, 3 pleasant, and 3 situations where someone might drink). These measures will be used to assess the influence of positive and negative current life events on drinking. d) Drinking motives: Participants will be asked to respond to 3-items for each of three drinking motives as to why they drank today and yesterday; to cope, to enhance or to socialize on a 3-point scale (1= "not at all", 2="somewhat" and 3="definitely).

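### The 3- and 6-month visits name serum for PEth, while the laboratory section places PEth in red-cell membranes, calls its specimen blood, and omits these two draws

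*Combined protocol and SAP*

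**What the plan says.** Section 2.C.4.d (visits 15 and 16) gives the purpose of the post-treatment visits: "To evaluate the durability of treatment effects". For the blood draw it specifies "Blood samples for measurement of serum PEth", together with 3α-diolG.

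Section 2.C.6.a (Laboratory/Medical Assessments) describes the analyte: "PEth is an alcohol-specific adduct catalyzed by phospholipase D from ethanol and phosphatidylcholine in membranes of red blood cells". On the specimen it says "Blood will be archived for measurement of phosphatidylethanol (PEth) by a commercial testing lab as an objective measure of alcohol use". On timing it says "Blood for PEth will be collected at screening, and weeks 6, 12, 18 and 24". The same section uses the word serum for 3α-diolG and for the steroid hormones, but not for PEth.

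Table 2 (Schedule of Assessments) has a row headed "Study outcome blood samples". It is marked at screening, weeks 6, 12, 18 and 24, and visits 15-16, and it names no specimen type.

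**The concern.** Serum is what is left once blood has clotted and the cells are removed. The protocol itself says PEth sits in the membranes of those cells. Read literally, the follow-up instruction asks for a sample that lacks the compartment carrying the analyte.

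What is at stake is the objective check on drinking after treatment ends. If follow-up PEth came from serum and earlier PEth from a sample containing red cells, the two sets could not be compared, and a low follow-up value could be mistaken for a lasting reduction in drinking. Site staff who turn to the laboratory section for guidance would find neither a named blood fraction for PEth nor any mention of the two follow-up draws.

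**Working it through.** No power, alpha or effect-size calculation applies, and the plan gives no figure on this point to reproduce. The check is a comparison of texts.

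**1. What each section says about the PEth specimen**

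| Place | Time points | Specimen wording for PEth |
|---|---|---|
| 2.C.4.a (screening visit) | screening | blood |
| 2.C.6.a | screening, weeks 6, 12, 18, 24 | blood, no fraction named |
| Table 2 (Schedule of Assessments) | the same five, plus visits 15-16 | blood, no fraction named |
| 2.C.4.d | months 3 and 6 | serum |

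Only 2.C.4.d names a fraction, and it is the only text that names a PEth specimen at follow-up. Nothing elsewhere overrides it, because the list in 2.C.6.a stops at week 24.

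**2. Time points.** 2.C.6.a lists 5. 2.C.4.d and Table 2 add 2, so 5 + 2 = 7. The serum wording touches 2 of 7, which is every post-treatment one.

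**3. Other drinking measures at visits 15-16.** The timeline follow-back interview, the alcohol section of the SCID, the problem inventory (SIP) and the craving scale (PACS) are all interview or self-report. The breath or saliva test in 2.C.4 is done only when two or more signs of intoxication are seen, and it reflects alcohol present at that moment. The urine screen is described as a test for drugs of abuse, and no alcohol marker is named for it. Repeat transaminases apply only to subjects with raised baseline values and stop at week 24. PEth is therefore the only scheduled objective measure of drinking at these visits.

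**4. Outcomes that use the follow-up samples.** Section 2.C.9.a.2 bases the primary outcomes on timeline follow-back reports. Its PEth outcome is the change from baseline to the end of each treatment phase, which uses the screening, week 12 and week 24 samples. None of these depends on a month 3 or month 6 sample.

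**5. How much of the follow-up period PEth could cover.** 2.C.6.a says PEth reflects the past 20-30 days. Taking each follow-up interval as about 90 days, that is 20/90 = 22% to 30/90 = 33%, or at most the last third.

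**The case against.** The strongest reply is that this is one misplaced adjective. The sentence in 2.C.4.d begins by calling for blood samples, the word serum heads a short list that also contains 3α-diolG (which is measured in serum), and the laboratory section speaks only of blood for PEth. That reading is plausible, and it lowers the chance that serum was ever drawn for PEth. It does not remove the need for a correction, because 2.C.4.d is a visit procedure and the only place that names a PEth specimen at follow-up.

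It is also fair to say that no defined outcome is lost. The analysis section sets out no post-treatment PEth analysis, and a valid sample would cover only part of each interval. Participants are also reminded to keep a written drinking diary, so follow-up reports need not rest on recall alone. All of this stands and limits the size of the point. The diary is still self-report.

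A reader might infer more than the documents support:

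- *That serum PEth would read near zero in everyone.* The documents give no assay values by specimen. They support only that such values may be uninterpretable.
- *That follow-up values are certain to be in a different matrix from earlier ones.* 2.C.6.a does not name the fraction used during treatment, so this is a risk and not a certainty.
- *That the loss can be counted from the phase 1 target of 160 completers.* That ignores attrition in phase 2 and the telephone follow-up that 2.C.4.d allows, which yields no blood.
- *That ACTH shows a second specimen mismatch.* Section 2.B.1 says "dutasteride would be expected to reduce the plasma ACTH to cortisol ratio", while 2.C.6.a lists ACTH among the serum assays. But 2.B.1 is background on mechanism, 2.C.4.a names the study ratio without a matrix, and the ratio is not an outcome in 2.C.9.a.2. Moving ACTH alone would also leave cortisol in the serum list.

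**Conclusion.** The inconsistency is real and internal to the protocol. The follow-up section names serum for an analyte that the laboratory section places in red-cell membranes, and the laboratory section's collection list leaves out the two follow-up draws altogether.

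The consequence is conditional. If the follow-up wording is applied literally, both post-treatment PEth measurements may be uninterpretable and not comparable with earlier ones, and the durability visits would then rest on self-report alone. If it is a slip and whole blood is drawn, the harm is confined to the text. The conclusion rests on the protocol's own account of where PEth is found and on the ordinary meaning of serum.

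The primary outcomes and the end-of-phase PEth outcome stand either way. The correction is worth making because it costs little, and a follow-up PEth result is easily misread if the specimen is wrong.

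**What to change.** 1. In 2.C.4.d, delete the word serum before PEth and keep it for 3α-diolG.
2. In 2.C.6.a, name one specimen that contains red cells (whole blood) for PEth at all seven time points, and add the 3- and 6-month visits to the collection list so that it agrees with 2.C.4.d and Table 2.
3. If follow-up samples have already been taken, check the laboratory records for the fraction kept. If only serum was kept, report this and do not interpret those PEth values as evidence of sustained reduction.

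The cost is wording in two sections and possibly a different tube at draws already scheduled. No visit or procedure is added.

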2.C.3.a. Dutasteride is FDA approved to treat prostatic hypertrophy and is a competitive and specific inhibitor of both type I and type II steroid 5α-reductase enzymes with which it forms a stable enzyme complex with very slow dissociation. In humans, type I 5AR is present in the brain, liver, adrenal gland, and adipose tissue and is responsible for onethird of circulating DHT. Type II 5AR is present in the liver and prostate, and is responsible for two-thirds of circulating DHT. For studies of alcohol use, inhibition of type I 5AR may be of particular importance, as type I 5AR, but not type II enzyme, is present in the adult brain (Lephart, Lund et al. 2001) where local generation of neuroactive steroids is thought to occur in addition to peripherally generated neuroactive steroids. The dutasteride dose of 1 mg/day proposed for this study is expected to achieve a >90% inhibition of peripheral type II 5AR and a 60% inhibition of type 1 5AR by 4 weeks for a total reduction in DHT of ≅ 80% by 4 wks based on pharmacokinetic models (Gisleskog, Hermann et al. 1998) and consistent with our observed 80% reduction in 3α-adiol glucuronide at 6 wks in our recently completed initial study in men using this dose. Dutasteride will be purchased commercially and over encapsulated using opaque capsules by the UConn Health Research Pharmacy Service. Pbo will be formulated to match the active medication. Subjects will take one 0.5 mg capsule of dutasteride or matching pbo during the first

treatment visit (baseline study visit 2) and at home on day 2 followed by two capsules daily for either 12 or 24 weeks (depending on treatment response). Similarly, subjects transitioning from placebo or dutasteride based on phase 1 non-response will be given one capsule of medication (dutasteride 0.5 mg or naltrexone 25 mg) during their first phase 2 study visit and day 2 of phase 2 followed by two capsules daily for 12 weeks.

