2.C.4.b. Visit 2 (Baseline Visit): 3-21 days after the screening visit, eligible subjects will return for their baseline visit. Subjects will be instructed in the use of study medication and will take one capsule study medication (0.5 mg dutasteride or pbo) at the baseline visit and again on study day 2, followed by 2 capsules daily for the remainder of the phase 1 12-week treatment period (in order to match capsule number for 2 day naltrexone titration in phase 2). Finally, subjects will be trained to use a paper calendar provided by staff to record their daily drinking and use of the IVR system to record their mood, desire to drink, self-efficacy and daily drinking during weeks 1-4 and 9-12 of phase 1 and 21-24 of phase 2. We considered asking subjects to use the IVR report daily for the 168 days of treatment but considered that this would be an excessive subject burden.

Study visits beyond visit 2, may be conducted remotely by telephone if a participant is unable to come to the clinic due to illness, travel, or other valid concerns (e.g. about exposure to COVID-19) related to traveling to UConn Health. Participants will be sent a one-time use REDCap secure link via email to complete study visit surveys. In the event a

participant is unable to attend an in person scheduled visit, backup supply of medication previously provided may be used or additional medication (up to 8 weeks) will be provided at an earlier visit if inability to attend future scheduled visit is anticipated in advance. Study staff will consult with study physician regarding whether study medication should be continued if a participant reports illness as reason for a missed in person visit. All unused medications will be brought to the next in person study visit.

2.C.4.c. Bi-weekly Clinic or remote Visits 3-14: A brief Timeline Follow-Back (TLFB) interview will be performed to track participants' daily alcohol consumption and medication use since the last study visit, and a trained staff member will deliver the medical management intervention.

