as to whether events occurred before age 6, between ages 6 and 17, above age 18 or within the past year. We previously reported an interaction of FKBP5 genotype and trauma measured with the TESI on drinking in a large college student sample (Lieberman, Armeli et al. 2016). Presence or absence of childhood trauma will be evaluated for main and interactive effects with FKBP5 genotype on predicting treatment outcomes; g) Adverse Child Experiences Scale (ACES) The ACES assesses early life stress in the form of childhood exposure to adverse experiences and a risky family environment (Felitti, Anda et al. 1998). This 17 item questionnaire probes childhood exposures including psychological abuse, physical abuse, sexual abuse, substance abuse within the family, mental illness within the family, violence toward mother, and criminal behavior in the household. Felitti et al. (Felitti, Anda et al. 1998) found that in a large sample of adults belonging to a HMO, more than half endorsed at least one category of childhood exposure. Individuals who had experienced four or more categories of childhood exposure had 4 to 12-fold increased risk for alcoholism, drug abuse, depression and risky sexual behavior. Scores for the ACES will be evaluated for main and interactive effects with the FKBP5 genotype on predicting treatment outcomes.

2.C.6.b.2. Areas assessed daily during the active treatment period: IVR will be used to collect daily subjective ratings of alcohol-related expectancies, craving, anxiety/tension, and self-efficacy to reduce drinking, as well as drinking amounts. To reduce subject burden for daily IVR in this 24-wk study, we will use IVR to capture daily data for the first 4 study weeks and the last 4 weeks of both phase 1 and phase 2. The IVR daily drinking data will be used together with bi-weekly drinking reports to determine treatment response (60% reduction in drinks/wk) during the last 4 weeks of phase 1 to inform treatment assignment for phase 2. Daily IVR reports will also enable us to address whether study medication moderates associations between daily mood, drinking motives, self-efficacy or daily events and drinking as has been reported using IVR methods for treatment with naltrexone and topiramate (Kranzler, Armeli et al. 2004, Armeli, Feinn et al. 2006). Moderation of relationships between daily mood reports and drinking by medication will be contrasted between baseline and end of phase 1 or 2.

Table 2: Schedule of Assessments

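### The daily-diary moderation contrast uses a 'baseline' that, in the randomised dutasteride arm, is already on drug, so any effect present early is subtracted; the amount is unknown

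*Combined protocol and SAP*

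**What the plan says.** Section 2.C.6.b.2 is headed "Areas assessed daily during the active treatment period". IVR is used there to "capture daily data for the first 4 study weeks and the last 4 weeks of both phase 1 and phase 2". Two sentences describe the analysis. The first is general: the daily reports will show whether study medication moderates the links of mood, motives, self-efficacy and events with drinking. The second names a contrast: "Moderation of relationships between daily mood reports and drinking by medication will be contrasted between baseline and end of phase 1 or 2". Baseline is not defined.

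Section 2.C.4.b sets the timing. At visit 2 subjects are trained on the IVR system, which covers "daily drinking during weeks 1-4 and 9-12 of phase 1 and 21-24 of phase 2". At that same visit they "will take one capsule study medication (0.5 mg dutasteride or pbo) at the baseline visit and again on study day 2".

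The schedule of assessments (Table 2) has no IVR mark at screening; the first is in the visit 2 column, where medication starts. The payment terms in section 3.A.1 cover the same three blocks of weeks. The data analysis section (2.C.9) contains no model, baseline definition or power statement for the IVR data.

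**The concern.** A contrast with baseline normally separates a treatment effect from the state before treatment. Here the dutasteride arm has no diary record of that state. If the drug weakens the link between mood and drinking within the first weeks, the effect sits in both windows being compared, and the change between them shows only what was added later. A small change could then be read as no moderation when moderation was present throughout.

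This matters because the daily diary is the plan's day-level look at the stress and coping mechanism put forward in section 2.B.2. The sections on dutasteride itself also give reason to expect early activity. Section 2.C.3.a anticipates a "60% inhibition of type 1 5AR by 4 weeks for a total reduction in DHT of" about 80%, and section 2.B.1 reports less drinking for 1-2 weeks after a single 4-mg dose.

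**Working it through.** **1. Is there any IVR week before dosing?** The payment figures in section 3.A.1 settle it.
- Phase 1: 7 calls × $2 + $6 = $20 per week; 8 weeks (1-4 and 9-12) = $160.
- Phase 2: 7 calls × $3 + $9 = $30 per week; 4 weeks (21-24) = $120.
- IVR total: $160 + $120 = $280, the stated maximum. Adding 12 visits × $20 and 2 follow-ups × $50 gives $620, the stated overall maximum.

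Both figures reproduce exactly with 12 on-treatment weeks, so no pre-dose week is scheduled or paid for.

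**2. Could another source supply a pre-dose slope?** The screening TLFB (section 2.C.4.a) gives 90 days of drinking amounts without daily mood. The first IVR call can recall one earlier day of drinking and motives, but the mood item is not described as covering the previous day. Neither yields a pre-dose mood-drinking slope.

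**3. What does the contrast estimate?** Let E(early) and E(late) be the between-arm differences in mood-drinking slope in the window used as baseline and in weeks 9-12. The change contrast estimates E(late) − E(early). The share of the late effect that it keeps is 1 − E(early)/E(late). A between-arm comparison within weeks 9-12 estimates E(late) itself.

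**4. How large is the loss?** The protocol gives no onset curve for this slope, so each row below is an assumption. Effects are averaged over days 1-28 (or days 1-7) and days 57-84.

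| Assumed onset | Kept, weeks 1-4 as baseline | Kept, week 1 as baseline |
|---|---|---|
| None before week 5, then full | 100% | 100% |
| Linear to day 84 | 79% | 94% |
| Linear to a plateau at day 28 | 48% | 86% |
| Exponential, 90% at day 28 | 37% | 73% |
| Linear to a plateau at day 14 | 23% | 71% |
| Immediate | 0% | 0% |

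Example for the third row: the mean of days 1-28 is 14.5, and 14.5/28 = 0.518. The late mean is 1, so the share kept is 1 − 0.518 = 0.482.

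**5. What would that do to power?** Illustration only, with the same standard error and two-sided α = 0.05: if a contrast keeping the full effect had 80% power, power at share r is Φ[r(1.960 + 0.842) − 1.960]. At r = 0.75 this is 56%; at r = 0.5 it is 29%.

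**6. Whose early window is on dutasteride?**
- Randomised dutasteride arm: yes. For non-responders later moved to naltrexone, the phase 1 windows precede naltrexone but are on dutasteride.
- Placebo arm: no. For placebo non-responders (64 expected in Table 1), weeks 1-4 and 9-12 are both before dutasteride and weeks 21-24 are on it.

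**The case against.** The strongest reply is that the general sentence in section 2.C.6.b.2 already allows a direct between-arm test, and that the specific sentence can be read as estimating moderation in each window and then comparing the estimates. On that reading a persistent early effect would be seen in both windows. This stands as a possible reading. But the change between windows is the only contrast actually named, and section 2.C.9 does not say which estimate carries the conclusion.

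Second, onset may be slow. The earlier trial (section 2.B.2) found treatment × time interactions, with the arms separating over the weeks, and section 2.C.9.a.2 allows for a weak response early in each phase. The evidence for early action concerns other quantities: enzyme inhibition reached by the end of week 4, and amount drunk after one dose in male social drinkers. None of it measures the mood-drinking slope. This stands too, and is why no single loss can be claimed.

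Third, baseline need not mean all of weeks 1-4. Week 1 alone would keep 71-94% under the gradual curves above. Table 2 also labels the week 12 visit as the phase 2 baseline, so weeks 9-12 may be meant for phase 2. These alternatives reduce the problem for some comparisons, but leave the choice open until the data are in hand. No choice of window gives the randomised dutasteride arm a pre-dose slope.

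**Conclusion.** The point holds in limited form. In the randomised dutasteride arm every IVR window is on treatment, so the stated early-to-late contrast subtracts whatever effect exists in the window called baseline. The share kept runs from 100% to 0% according to the assumed onset, with about half kept if the effect builds linearly to week 4.

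A reader might infer three stronger things that the documents do not support:
- That half the effect is lost and four times the information is needed (1/0.5² = 4). This follows only from one assumed curve.
- That the whole diary analysis lacks a drug-free reference. Placebo non-responders have two such windows.
- That the trial's efficacy result is affected. The primary outcomes, HDD/wk and SD/wk, come from TLFB and are adjusted for pre-treatment TLFB (section 2.C.9.a.2). The diary moderation analysis appears in no specific aim and has no power claim.

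It is a low-cost improvement to a secondary mechanistic analysis.

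**What to change.** In section 2.C.6.b.2, with a matching entry in 2.C.9, before the IVR data are analysed by arm:

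1. Make the between-arm difference in mood-drinking slope (the medication × mood term) within weeks 9-12 the main phase 1 estimate.
2. Call weeks 1-4 early treatment instead of baseline, and report the change from weeks 1-4 to weeks 9-12 only as a secondary time-course result.
3. For placebo non-responders switched to dutasteride, use weeks 1-4 and weeks 9-12 together as the pre-dutasteride reference for weeks 21-24. Add a caution about regression to the mean: non-response is defined by drinking in weeks 9-12, so that window would be a selected reference if used alone.

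These are wording changes and need no new data.

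A pre-dose IVR period is optional and not needed for the fix. It would mean training at screening and could help only participants not yet dosed. It would not give a full 7 days when visit 2 falls 3-6 days after screening. At the phase 1 rate a completed week costs $20. If all 260 people enrolled at screening completed it, that is 260 × $20 / 190, or about $27 per randomised participant. Daily self-monitoring before dosing might also lower drinking somewhat, though equally in both arms.
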